### **4.1 Removal of Subjects**

Subjects have the right to withdraw from the study at any time and for any reason without prejudice to his or her future medical care by the physician or at the institution. Withdrawal of consent for a study means that the subject does not wish to or is unable to continue further study participation; subject data up to withdrawal of consent will be included in the analysis of the study. Any subject may withdraw consent to participate in the study at any time during the study. Should a subject (or a legally acceptable representative) request or decide to withdraw from the study, all efforts will be made to complete and report the observations as thoroughly as possible up to the date of withdrawal. All information should be reported on the applicable eCRFs.

Reasons for removal from observation might include but is not limited to:

- withdrawal of consent
- administrative decision by the investigator or Amgen
- death
- lost to follow-up

### **4.2 Replacement of Subjects**

No replacement of subjects will be permitted.

### **4.3 Internal Validity of Study Design**

#### **4.3.1 Selection Bias**

We do anticipate some degree of selection bias within our study. Since we are not recruiting patients until they have been dosed with Vectibix® at least once, there is a

small group of patients who we will not be sampling ie, those who do not commence treatment, or cease treatment very soon after the first dose, usually because of death or disease progression. Therefore the response rate may be inflated slightly and other collected data impacted. Note that in Germany we may only be able to obtain limited data from deceased patients. However generally for most patients this will not limit inclusion of patient data into the study as the study is mainly prospective in design and patients will be alive at study enrolment (where consent is required). Should subjects die during the course of the study it may become more difficult to obtain complete follow up information if the notes are then subsequently filed elsewhere and we need informed consent to obtain them.

#### **4.3.2 Reliability and Validity**

Abstractors will be trained to not make interpretations of data. The CRF will be developed to avoid interpretation and only abstract data as documented in the record. Measures will be put in place in order to ensure that the data are as reliable as possible. There will be frequent data transfers throughout the study period and data checks to test data quality.

#### **4.4 External validity**

We shall represent different types of hospitals and outpatient departments (academic, specialist, general hospitals etc) in this study. We will be performing frequent data extractions to review any inconsistencies within the data and minimize the effect of bias. Centre selection bias is a potential threat to representativeness of the subject population included in the study. We aim to include a wide selection of hospital types that include large specialist referral centres as well as smaller general hospitals and each country will be required to include a representative sample of different types of hospitals (academic, specialist, general hospitals, etc). In Germany many patients may also be treated in an outpatient oncology clinic setting so we represent these centres too.

### **5. STATISTICAL CONSIDERATIONS**

#### **5.1 Study Size**

This study will enrol approximately 740 subjects (up to 350 in France and up to 390 in Germany) in total. Enrolment into the study will be capped by country according to these numbers. Statistical properties of the study size are described in [Section 5.3](#). These samples sizes are consistent with previous submissions to reimbursement agencies.

---

## 5.2 Study Outcomes, Subsets, and Covariates

### 5.2.1 Outcomes

#### Primary:

- Treatment pattern of Vectibix® and concomitant chemotherapy for mCRC will be described, including information on
  - Type of chemotherapy combined with Vectibix® in the first or second line setting
  - Starting dose and dose administration schedule of Vectibix® and chemotherapy
  - Cumulative dose, maximum dose, duration of exposure and total number of infusions received from the initiation of Vectibix® therapy and chemotherapy
  - Dose reductions and delays and reason(s) for dose reduction and delays of Vectibix® and/or concomitant chemotherapy
  - Discontinuation and reason(s) for discontinuation of Vectibix® and chemotherapy

#### Secondary:

- The following will be described and tabulated
  - Healthcare resource utilization, including type of visit (inpatient, outpatient, ER, other) and reason for hospitalisation
  - Demographics, disease characteristics, co-morbidities, individual treatment goals and prior treatment history
  - Response to Vectibix®, if documented, including best response, conversion to resectability, and by individual treatment goals
  - Summaries of planned anti-cancer treatment post initiation post Vectibix® discontinuation

### 5.2.2 Analysis Subsets

First Line FOLFOX Analysis Set (FLFAS): all enrolled subjects who have received at least one infusion of Vectibix® in combination with FOLFOX as first-line treatment, a maximum of 42 days before entering study.

Second Line FOLFIRI Analysis Set (SLFAS): all enrolled subjects who have received at least one infusion of Vectibix® in combination with FOLFIRI as second-line treatment and have received first-line fluoropyrimidine-based chemotherapy (excluding irinotecan), a maximum of 42 days before entering study.

FLFAS and SLFAS are the primary analysis sets for all analyses. Selected sensitivity analyses may be performed to assess the impact of using other analysis sets.

The data will be summarized by country to fulfil local post reimbursement requirements.

---

### 5.2.3 Covariates

Certain pre-treatment factors (covariates) may be found to affect the pattern of Vectibix® usage, hence subgroup analysis will be used to investigate the covariates listed below with a view to a numerical evaluation of their influence.

The following covariates may be used to conduct the subgroup analyses for all subjects:

- ECOG performance status: ≤1 vs. 2
- Location of primary tumour: colon vs. rectum, right or left
- Number of sites of metastatic lesions: 1 vs. 2 vs. ≥3 and per organ (liver, lung, other etc)
- Location of sites of metastatic disease: liver only vs. other sites ± liver
- Prior adjuvant therapy: yes vs. no (regimen and date last adjuvant treatment administered)
- Type of centre
- Individual treatment goals (including resectability)
- The following covariates may be used to conduct the subgroup analyses for SLFAS:
- Categories of prior systemic therapy mCRC: chemotherapy only vs. chemotherapy plus targeted therapy
- Prior anti-EGFR therapy for mCRC : yes vs. no
- Prior anti-VEGF therapy for mCRC: yes vs. no
- Prior oxaliplatin-based chemotherapy for mCRC: yes vs. no
- Prior irinotecan-based chemotherapy for mCRC: yes vs. no

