### **3.1 Number of Centres**

Approximately 50-100 centres will participate in this study in total. A large number of centres are necessary to ensure we capture sufficient patients as the change in the label for Vectibix® in Europe is relatively recent. Centres that do not enrol subjects within 3 months of centre initiation may be closed if it is likely that they will not be able to enrol a sufficient number of subjects in the required timeframe. We aim to include a wide selection of hospital types that include large specialist referral centres as well as smaller general hospitals and each country will be required to include a representative sample of different types of hospitals (academic, specialist, general hospitals, private etc). In Germany many patients may also be treated in an outpatient oncology clinic setting so we represent these centres too.

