#### 5.6 Planned Methods of Analysis

##### 5.6.1 General Approach/Considerations

The analysis of this study will be descriptive in nature. The data will be summarized for subjects with metastatic colorectal cancer (mCRC) with tumour expressing wild-type (non-mutated) *KRAS* who received Vectibix® in combination with FOLFOX as first-line

---

treatment and subjects who received Vectibix® in combination with FOLFIRI as second-line treatment and received first-line fluoropyrimidine-based chemotherapy (excluding irinotecan). The data will be summarized by country to fulfil local post reimbursement requirements. For continuous outcomes, the mean, standard deviation, median, and range will be provided. For categorical variables, the frequency and percentage, with two-sided 95% CI, will be displayed for the treatment pattern of Vectibix®. Summary tables and analyses will be based on FLFAS and SLFAS and corresponding local tumour response analysis sets.

For each outcome parameter, the covariates listed in [Section 5.2.3](#) will be assessed in a logistic or general linear model. Non-significant factors will be eliminated stepwise until only covariates significant at the 5% level remain, thereby indicating which covariates have an important influence on treatment pattern. Summary statistics will then be reported for each level of the significant covariates.

Selected sensitivity analyses may be performed to assess the impact of protocol deviations using other analysis sets.

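### The stepwise covariate models omit country and do not say whether they are fitted within country, so a pooled fit could credit a country difference to another covariate such as type of centre

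*Protocol*

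**What the plan says.** Section 5.2.3 of the protocol introduces its main list with "The following covariates may be used to conduct the subgroup analyses for all subjects". The list covers performance status, tumour location, metastatic sites, prior adjuvant therapy, "Type of centre" and treatment goals. A further list applies to the second-line set only. Country is in neither.

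Section 5.6.1 says that for each outcome these covariates "will be assessed in a logistic or general linear model". It then fixes the selection rule: "Non-significant factors will be eliminated stepwise until only covariates significant at the 5% level remain". The survivors are read as the factors that matter for treatment pattern, and "Summary statistics will then be reported for each level of the significant covariates".

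Country enters Section 5.6.1 through one sentence on reporting: "The data will be summarized by country to fulfil local post reimbursement requirements". Section 5.2.2 defines the two analysis sets, FLFAS and SLFAS, by line and regimen for all enrolled subjects. It makes them the primary sets for every analysis and does not restrict either set by country.

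On the centre mix, Section 3.1 says "In Germany many patients may also be treated in an outpatient oncology clinic setting so we represent these centres too". The same section requires each country to cover a representative range of hospital types.

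**The concern.** The protocol fixes the covariate list, the elimination rule and the interpretation of what is left, but not whether the two countries are modelled together. Country is structural elsewhere: enrolment is capped by country, Table 1 is laid out by country, and the summaries are by country.

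If FLFAS or SLFAS is modelled across both countries without a country term, any covariate whose distribution differs between France and Germany stands in partly for country. It can then survive at 5% because prescribing or dosing practice differs between the countries, although it has no effect within either. The report would present it as an influence on treatment pattern and tabulate results by its levels. Readers at the reimbursement agencies, and readers in the neighbouring countries to which Section 6 expects the results to extend, could take a national difference for a difference between kinds of centre.

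**Working it through.** **No figure in the protocol to reproduce.** The protocol gives no number for this point. The nearest are the Table 1 half-widths for all subjects at a proportion of 0.5: 1.96 × √(0.25/350) = 5.24% (printed 5.2%) and 1.96 × √(0.25/390) = 4.96% (printed 5.0%). They reproduce, but they bear on the point only in showing that precision was planned by country.

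**Inputs from the protocol**
- Sample sizes of 350 (France) and 390 (Germany), Section 5.1.
- First-line share of about 60%, Section 5.3. FLFAS: 0.60 × 350 = 210 and 0.60 × 390 = 234. SLFAS: 0.40 × 350 = 140 and 0.40 × 390 = 156. (Table 1 prints 172 for the German second-line group, which does not match 40% of 390; 156 is used here.)
- Retention at 5%, Section 5.6.1, taken as two-sided.

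**Assumptions, not in the protocol**
- Outpatient clinic is a level of the centre-type covariate.
- Clinic share is 5% to 30% in France and 30% to 60% in Germany.
- A binary outcome occurs in 30% of French subjects and 30% to 50% of German subjects.
- The outcome depends on country only; centre type has no effect.

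**Apparent effect in a pooled model, one case.** Take FLFAS, clinic share 10% in France and 50% in Germany, outcome 30% and 50%.
- Clinic subjects: 21 French and 117 German. Rate = (21 × 0.30 + 117 × 0.50)/138 = 64.8/138 = 0.470.
- Hospital subjects: 189 French and 117 German. Rate = (189 × 0.30 + 117 × 0.50)/306 = 115.2/306 = 0.376.
- Odds ratio = (0.470/0.530)/(0.376/0.624) ≈ 1.47, although the true within-country odds ratio is 1.

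**How often centre type is retained.** Each scenario had 1,000 simulated data sets and a logistic model with centre type as the only covariate, tested at 5%. The Monte Carlo standard error at 5% is √(0.05 × 0.95/1000) = 0.7 points. The table shows the pooled model without country.

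| Clinic share, France / Germany | Outcome, France / Germany | Apparent odds ratio | FLFAS | SLFAS |
|---|---|---|---|---|
| 20% / 30% | 30% / 40% | 1.06 | 7% | 5% |
| 20% / 30% | 30% / 50% | 1.12 | 8% | 8% |
| 10% / 30% | 30% / 40% | 1.14 | 9% | 7% |
| 10% / 30% | 30% / 50% | 1.28 | 16% | 15% |
| 10% / 50% | 30% / 40% | 1.22 | 15% | 13% |
| 10% / 50% | 30% / 50% | 1.47 | 44% | 33% |
| 5% / 60% | 30% / 40% | 1.30 | 27% | 18% |
| 5% / 60% | 30% / 50% | 1.65 | 71% | 53% |

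When the clinic share is equal in both countries, or the outcome rate is, the same model retains centre type in 4% to 7% of runs. With country added it is 4% to 6% in every scenario. Fitted on Germany alone it is 3% to 6%.

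A second set of assumptions for FLFAS used a 40% outcome in France and 3,000 runs per scenario. A 15-point country difference gave 20% (clinic shares 10% and 40%) and 34% (5% and 50%). A 20-point difference gave 31% and 54%. With country in the model all four were about 5%.

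These runs test centre type alone, not the full multi-covariate elimination, and treat subjects as independent within centres. They show the mechanism and its possible range and do not predict what this study will find.

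**The case against.** The strongest objection is that pooling is nowhere stated. The summaries are by country, Section 5.3 sizes the subgroups in each country, Table 1 has no combined column, and the by-country sentence in Section 5.6.1 comes just before the model paragraph. Models fitted within country have no country confounding, and that may be what is meant. It is also a choice that a statistical analysis plan often settles.

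Part of this stands: a reader might infer that the protocol prescribes pooled models, and it does not. But the by-country sentence governs summaries, the model paragraph has no such qualifier, and the analysis sets on which the analyses rest span both countries. The protocol also fixes the covariates and the selection rule itself, so an analysis plan that pooled the countries and followed that list would have no country term.

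The second objection is that centre type has not been shown to differ by country. This stands. A reader might infer a known imbalance, but Section 3.1 says only that many German patients may also be treated in outpatient clinics. It gives no shares and no French counterpart, and it requires a representative mix of hospital types in each country. Section 3 admits inpatient and outpatient centres in both countries. The levels of the centre-type covariate are not defined, and the baseline data list in Section 4 names treatment setting alongside centre type, so outpatient clinic may not be one of its levels.

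Third, Section 5.2.3 says only that the covariates may be used, and the study is descriptive with no hypothesis test. That limits what is at stake. Even so, Section 5.6.1 says that the covariates will be assessed, and lets the result decide which subgroup tables appear and which factors are called influential.

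**Conclusion.** The point holds as a gap in a stated model. The covariate list feeding the stepwise models omits country, and the protocol does not say that the models are fitted within country. If they are pooled, as the analysis-set definitions suggest, a covariate whose mix differs by country can be retained because of a country difference in practice. Type of centre is a possible example, not an established one.

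The size cannot be derived from the protocol. Under the assumed shares and rates, false retention of centre type runs from about 5% (no imbalance or no country difference) to well above 20% (large imbalance), against about 5% with country in the model. The documents support neither end of that range over the other. The primary by-country descriptive summaries are unaffected, so this is a low-cost improvement and not a threat to the main results.

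**What to change.** Add one sentence to Section 5.6.1, choosing one of two forms:
- Country is included in every pooled logistic or general linear model as a forced term, not subject to stepwise removal.
- The models are fitted separately for France and Germany, as the summaries are.

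The first costs one degree of freedom per model and no new data, since country is known for every subject. The second removes the confounding completely, but each model then rests on one country's subjects: about 210 or 234 in first line and 140 or 156 in second line. It may also retain different covariates in the two countries. Either form closes the gap.

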### 5.3 Sample Size Considerations

The analysis of this study will be descriptive in nature. Consequently, the sample size has not been assessed in terms of statistical power but with regards to what precision might be expected when examining categorical data such as type of anticancer therapy and discontinuation of Vectibix®. Proportions and confidence intervals will be most useful if reported in subgroups rather than overall. For instance the majority (perhaps 60%) of subjects recruited will be receiving first line treatment; their treatment patterns are expected to be different from second line subjects. Similarly, first line subjects with potentially resectable tumours (around 20%) will have different treatment patterns to those with unresectable tumours. Thus, we will have three important subgroups (the number of resectable subjects in the second line is expected to be negligible), consisting of 12% (line 1 potentially resectable), 48% (line 1 unresectable) and 40% (line 2) of the subjects in each country.

Table 1 below lists the expected precision of binomial estimates (in terms of half-width of a 95% confidence interval) using the planned sample sizes in the above scenarios. The expected precision in most of the subsets will be smaller than 10% but could be as high around 15% in Line 1 potentially resectable subjects.

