### **3.2 Number of Subjects**

Participants in this observational study shall be referred to as “subjects”. This study will enrol approximately 740 subjects (up to 350 in France and up to 390 in Germany) in total. Enrolment into the study will be capped by country according to these numbers.

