### **3.4 Subject Eligibility**

Before any study-specific data are recorded, the appropriate written informed consent must be obtained if required. The decision to prescribe treatments must have been freely undertaken by the clinician prior to consideration for the subject to be included in the study. Therefore, treatment administration will be independent and dissociated from participation in the study.

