**3.8 Concomitant Therapy**

Throughout the study, investigators may prescribe any concomitant medications or treatments deemed necessary to provide adequate supportive care. There are no proscribed therapies and investigators may treat their subjects according to clinical practice.

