**Table 1. Expected Precision for the Proportion of Treatment Patterns**

Expected Proportion of Treatment Pattern	Half-width of 95% CI for Proportion of Subjects with a Treatment Pattern			
	France (350 subjects)			
	Line 1 resectable (n=42)	Line 1 unresectable (n=168)	Line 2 resectable (n=140)	All subjects (n=350)
0.1	9.1%	4.5%	5.0%	3.1%
0.3	13.9%	6.9%	7.6%	4.8%
0.5	15.1%	7.6%	8.3%	5.2%

Expected Proportion of Treatment Pattern	Half-width of 95% CI for Proportion of Subjects with a Treatment Pattern			
	Germany (390 subjects)			
	Line 1 resectable (n=47)	Line 1 unresectable (n=187)	Line 2 resectable (n=172)	All subjects (n=390)
0.1	8.6%	4.3%	4.5%	3.0%
0.3	13.1%	6.6%	6.8%	4.5%
0.5	14.3%	7.2%	7.5%	5.0%

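### Table 1 assumes independent subjects although they are recruited through 50-100 centres, so the stated precision is optimistic under any positive within-centre correlation

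*Protocol*

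**What the plan says.** Section 5.3 sets aside power and rests the study size on expected precision: "Table 1 below lists the expected precision of binomial estimates (in terms of half-width of a 95% confidence interval) using the planned sample sizes". Table 1 gives those half-widths by country for assumed proportions of 0.1, 0.3 and 0.5. The subgroup sizes come from a split "consisting of 12% (line 1 potentially resectable), 48% (line 1 unresectable) and 40% (line 2) of the subjects in each country". The section concludes that precision is below 10% in most subsets and around 15% for line 1 potentially resectable subjects.

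On recruitment, section 3.1 says "Approximately 50-100 centres will participate in this study in total", and section 3.2 says "This study will enrol approximately 740 subjects (up to 350 in France and up to 390 in Germany". On treatment, section 3.4 says "The decision to prescribe treatments must have been freely undertaken by the clinician", and section 3.8 adds that "investigators may treat their subjects according to clinical practice".

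For the analysis, section 5.6.1 says "For categorical variables, the frequency and percentage, with two-sided 95% CI, will be displayed for the treatment pattern of Vectibix", without a method for the interval. The same section puts the covariates of section 5.2.3, among them the type of centre, into a logistic or general linear model with stepwise elimination at the 5% level. Neither section 5.3 nor section 5.6.1 mentions within-centre correlation.

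**The concern.** A binomial half-width is correct when subjects are independent. Here they arrive in groups of about 7 to 15 per centre (740/100 = 7.4; 740/50 = 14.8). The primary outcomes include starting dose, schedule, dose reductions and delays, and discontinuation, which depend at least partly on the treating clinician. Two subjects from one centre may therefore resemble each other more than two subjects from different centres. In that case each subject carries less information than Table 1 assumes.

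Table 1 is the only statistical argument for the study size, and it does not state independence as an assumption. A reimbursement body that reads the country columns would expect tighter estimates than the design may deliver.

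The covariate model raises a related issue. Type of centre is constant within a centre. If subjects within a centre are correlated, an ordinary model understates the standard error of that term, and stepwise selection at 5% would retain it too often.

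**Working it through.** **Inputs from the protocol.** Two-sided 95% level (z = 1.96); proportions 0.1, 0.3 and 0.5; the subgroup sizes printed in Table 1; 50-100 centres in total.

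**Assumptions not in the protocol.** ICC of 0.02, 0.05 or 0.10; 25 to 50 centres in each country; equal centre sizes.

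**Step 1: reproduce Table 1.** Half-width = 1.96 × √(p(1−p)/n). At p = 0.5 for France:
- n = 350: 1.96 × √(0.25/350) = 5.24% (printed 5.2%)
- n = 168: 7.56% (printed 7.6%)
- n = 140: 8.28% (printed 8.3%)
- n = 42: 15.12% (printed 15.1%)

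All 24 cells for both countries reproduce to the printed decimal from the printed n. The table therefore uses a design effect of exactly 1.

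**Step 2: allow for clustering.** Design effect = 1 + (m − 1) × ICC, where m = n / number of centres, and not below 1. The half-width is multiplied by the square root of the design effect. For France, all subjects, m is 350/50 = 7 to 350/25 = 14. At ICC 0.05 the design effect is 1 + 6 × 0.05 = 1.30 to 1 + 13 × 0.05 = 1.65. The half-width is 5.24 × √1.30 = 6.0% to 5.24 × √1.65 = 6.7%.

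France, p = 0.5; each range runs from 50 to 25 centres:

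| Column | m | Printed | ICC 0.02 | ICC 0.05 | ICC 0.10 |
|---|---|---|---|---|---|
| All subjects (350) | 7-14 | 5.2% | 5.5-5.9% | 6.0-6.7% | 6.6-7.9% |
| Line 1 unresectable (168) | 3.4-6.7 | 7.6% | 7.7-8.0% | 8.0-8.6% | 8.4-9.5% |
| Line 2 (140) | 2.8-5.6 | 8.3% | 8.4-8.7% | 8.6-9.2% | 9.0-10.0% |
| Line 1 resectable (42) | 0.8-1.7 | 15.1% | 15.1-15.2% | 15.1-15.4% | 15.1-15.6% |

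Germany, all subjects (n = 390, m = 7.8-15.6, printed 5.0%) behaves the same way: 5.7-6.5% at ICC 0.05 and 6.4-7.8% at 0.10. Unequal centre sizes would widen all these figures further.

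**Step 3: what the printed width would cover.** If an interval had the width of Table 1 and the design effect were as above, its coverage would be 2Φ(1.96/√DE) − 1. For France, all subjects, this is about 87-91% at ICC 0.05 and 80-88% at 0.10.

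**Step 4: when the below-10% statement fails.** Solve half-width × √DE = 10% at p = 0.5 for the ICC.
- France line 2: DE must reach (10/8.28)² = 1.46. With 25 centres (m = 5.6) that needs ICC = 0.46/4.6 ≈ 0.10. If 50 centres are split in proportion to enrolment, France has about 24 (50 × 350/740) and the limit is about 0.09. With 50 centres in France (m = 2.8) it is about 0.25.
- France line 1 unresectable: DE must reach (10/7.56)² = 1.75. With 25 centres (m = 6.72) the limit is about 0.13, and with 50 centres about 0.32.

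**The case against.** The strongest reply has five parts.

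1. **The interval method is not fixed in the protocol.** A reader might infer that the planned 95% intervals ignore centre. The protocol does not support this: section 5.6.1 promises an interval and names no method, and that choice is commonly left to the SAP, which is not at hand. This part of the objection stands in full. The coverage figures above describe an interval as narrow as Table 1, not the intervals that will be reported.

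2. **The ICC is unknown.** Nothing in the documents makes 0.05-0.10 more plausible than 0.02, where the widening is at most 0.7 points in the columns above. This stands as a limit on the size of the effect. It does not rescue the table, because an ICC of zero is also an assumption, the most favourable of those considered, and it is not stated.

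3. **The protocol's conclusion mostly holds, and the largest change is in the all-subjects column.** Section 5.3 itself says subgroup intervals are more useful than overall ones, and the primary analysis sets are defined by line of treatment. This stands. The effect in the subgroup columns is modest. The country totals still matter because section 5.2.2 plans by-country summaries for reimbursement purposes.

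4. **Some outcomes are driven by the patient.** Section 4.3.1 attributes very early cessation mainly to death or progression, and eligibility fixes the regimen for each line. The ICC may therefore be small for discontinuation and larger for starting dose and schedule. This is a fair reason to show a range.

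5. **Type of centre is a category and does not prove correlation within individual centres.** This is correct. It matters here only because section 5.6.1 tests it, and it varies only between centres.

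**Conclusion.** The point holds for Table 1. The table assumes independent subjects without saying so, and its precision is optimistic under any positive ICC wherever a centre contributes more than one subject to a column. On the stated assumptions, the half-width at p = 0.5 grows by about 14-28% for France as a whole at ICC 0.05 (√1.30 to √1.65). At the same ICC it grows by about 6-13% for line 1 unresectable (√1.12 to √1.29) and 4-11% for line 2 (√1.09 to √1.23). For line 1 resectable the growth is at most about 3%, even at ICC 0.10 (√1.07).

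Two stronger readings are not supported. It is not shown that the analysis intervals will under-cover. Nor is the below-10% statement for most subsets shown to be wrong: it largely survives unless the ICC is about 0.09 or more with few centres. The direction is certain given a positive ICC, but the size is known only as a range. This is worth correcting and does not threaten the study.

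**What to change.** In section 5.3, state under Table 1 that the half-widths assume no within-centre correlation, and add half-widths for ICC 0.02, 0.05 and 0.10 with the assumed number of centres per country.

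In section 5.6.1, specify that the 95% intervals for treatment-pattern proportions, and the logistic or general linear covariate models that include type of centre, use centre as the cluster, for example through a cluster-robust variance or GEE.

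The cost is a note and a few extra rows in section 5.3, a sentence in section 5.6.1 carried into the SAP, slightly less favourable stated precision and a little more analysis work. No additional subjects are needed.
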